Old Text	
18.1 HANDLING OF SUBJECTS’ TEMPORARY TREATMENT DISCONTINUATION OR TERMINATION
 
For all subjects reaching the end of the trial (completed 5 year visit, death, or explant) or in case of premature withdrawal as described in section 8.5.5 (lost-to-follow-up, or subject’s decision) a trial termination form will be filled out in order to document the date and reason for discontinuation. Subjects who had their valves explanted will still have to be followed at least till 1 year primary endpoint.
 
Every attempt must be made to have all subjects complete the follow-up visit schedule. A subject will be considered lost to follow-up when all efforts to obtain information are unsuccessful. At a minimum, the effort to obtain information must include attempts to make contact via phone, and/or a certified letter should be sent to the subject’s last known address. Both phone contacts and copy of the letter must be documented/available in the subject’s medical record and recorded in the eCRF.

New Text	
18.1 HANDLING OF SUBJECTS’ TEMPORARY TREATMENT DISCONTINUATION OR TERMINATION
 
For all subjects reaching the end of the trial (completed 5 year visit, death, or explant) or in case of premature withdrawal as described in section 8.5.5 (lost-to-follow-up, or subject’s decision) a trial termination form will be filled out in order to document the date and reason for discontinuation. Subjects who had their valves explanted will still have to be followed at least till 1 year primary endpoint.
 
Every attempt must be made to have all subjects complete the follow-up visit schedule. A subject will be considered lost to follow-up when all efforts to obtain information are unsuccessful. At a minimum, the effort to obtain information must include attempts to make contact three contacts via phone, and/or a one certified letter should be sent to the subject’s last known address. Both phonePhone contacts and copy of the letter must be documented/available in the subject’s medical record and recorded in the eCRF.

Change 14	
CIP Section	19.3.1
Justification	Introduction of the need to have the process of patient consent documented in the source documentation of the hospital

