8.5.5 CRITERIA FOR SUBJECT TERMINATION

All enrolled subjects will be followed until the end of the trial except upon premature discontinuation in the trial.

Participation of a subject in the trial should be discontinued when:

- The exclusion from the trial is required for the subject's safety;
- Relevant Ethics Committee and/or regulatory authority withdraw approval(s)
- The subject decides to withdraw from the trial
- The subject is deemed lost to follow up

The subject may withdraw his/her consent or cooperation (i.e. the subject refuses to participate further in the trial) at any time without jeopardizing the normal standard of care.

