18 HANDLING OF TRIAL DISCONTINUATIONS

18.1 HANDLING OF SUBJECTS' TEMPORARY TREATMENT DISCONTINUATION OR TERMINATION

For all subjects reaching the end of the trial (completed 5 year visit, death, or explant) or in case of premature withdrawal as described in section 8.5.5 (lost-to-follow-up, or subject's decision) a trial termination form will be filled out in order to document the date and reason for discontinuation. Subjects who had their valves explanted will still have to be followed at least till 1 year primary endpoint.

Every attempt must be made to have all subjects complete the follow-up visit schedule. A subject will be considered lost to follow-up when all efforts to obtain information are unsuccessful. At a minimum, the effort to obtain information must include attempts to make three contacts via phone, one certified letter should be sent to the subject's last known address. Phone contacts and copy of the letter must be documented/available in the subject's medical record.

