5.2. DESCRIPTIVE STATISTICS

Descriptive statistics will be calculated using as reference the number of subjects in the relevant analysis population (any exception will be specified) according to the nature of the data as follows:

- Continuous variables: number of non-missing observations, arithmetic mean, standard deviation, minimum and maximum values, median and quartiles. If there are less than 5 observations, only the number of non-missing observations, arithmetic mean, median, minimum and maximum will be presented.
- Categorical variables: Number of missing and non-missing observations the relevant percentage on the analysis population. In case of subcategories, the relative frequencies will be calculated on the basis of the subjects in the subcategory, in this case a footnote will be added explaining the different denominators.
- Time-to-event variables: number of non-missing observations, minimum, first quartile, median including 95% confidence interval, third quartile, and maximum. For calculating the survival estimate CI bounds the log-log transformed estimate of CI bounds will be used. In addition, Kaplan-Meier estimates and plots will be provided with:
 - the 95% confidence interval bounds calculated per the method proposed by Greenwood⁸
 - the respective number of patients at risk and Kaplan-Meier estimates at different time points (at least every 5 months or more frequently)
 - the median and its 95% confidence interval.
 - the log-rank test p-value
 - the Hazard Ratio (HR), its 95% confidence interval and the relevant p-value.

Subjects ongoing and who are free from event at the analysis cut-off date will be censored at the analysis cut-off date. Subjects who have discontinued without an event will be censored at the date of discontinuation.

- For Bayesian analyses: posterior means, standard deviations, and 95% credible intervals will be reported.

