10.4. SENSITIVITY ANALYSES

The primary analysis will be assessed in sensitivity analyses using different assumptions and populations:

- the primary analysis will be repeated on the mITT population. For this analysis, missing data for the primary endpoint will be imputed using the same procedure used for the interim analysis (see Section 15). This analysis will be performed to assess the robustness of the results to protocol deviations: mITT analysis provides a “real life” scenario, in which participants may not comply to the protocol.
- the proportion of subjects that are event-free at one year will be estimated by means of a logistic regression model including as covariates the implanted valve groups (Perceval or standard sutured stented valves) and the stratification factors:

- country, and
- surgical approach.

This method allows to assess the sensitivity of non-inferiority results to possible confounding impact of the stratification factors.

A 97.5% one-sided upper confidence limit will be computed from the logistic model for the difference ($MACCE_{CONTROL} - MACCE_{PERCEVAL}$). The non-inferiority of Perceval to the Control will be confirmed if the upper confidence limit is lower than 0.05 (Δ). This sensitivity analysis of non-inferiority will be assessed in the Per Protocol Population.

- the one-year freedom from MACCE will be evaluated using the Kaplan-Meier estimates for cumulative freedom from MACCE and the Greenwood standard errors for each arm (as planned in the CIP before amendment). A 97.5% one-sided upper confidence limit will be computed for the difference ($MACCE_{CONTROL} - MACCE_{PERCEVAL}$) where $MACCE_j$ is the survival estimated by the Kaplan-Meier algorithm for arm j. The Perceval arm will be confirmed not inferior to the Control if the upper confidence limit is lower than 0.05 (Δ).

The test statistic is

$$\frac{MACCE_{PERCEVAL} - MACCE_{CONTROL} + \Delta}{\sqrt{VAR(MACCE_{PERCEVAL}) + VAR(MACCE_{CONTROL})}}$$

where VAR()s are the variances estimated by Greenwood's formula. The null hypothesis will be rejected if the test statistic is greater than 1.96. This sensitivity analysis of non-inferiority will be assessed both in PP and mITT populations in order to confirm the robustness of results to statistical method and protocol deviations.

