MACCE @ n year (Yes/No)	
CEC adjudication of Serious Adverse Event (SAE), Valve re-intervention:
 
YES if at least one per CEC:
 
 - Death (Time to SAE <=n*365.25 days) - Myocardial infarction (Time to SAE <= n*365.25 days) per CEC - Stroke (Time to SAE <= n*365.25 days) per CEC - Reintervention (Time to SAE <= n*365.25 days) 
NO, otherwise

PM implant	
SAE FORM – TREATMENT
 
Yes if:
 
 - Was a pulse generator implanted? = YES - If yes, specify = Pacemaker 
NOTE: PM implant will be classified as intraoperative, early or late according to the date of PM implant (not the AE start date)

Derived variable	Derivation algorithm
Last exposure date	
Study Termination, Serious Adverse Event (SAE):
 
 1. For explant of investigational device: date of explant 2. For dead subjects: date of death 3. For alive and not explanted subjects: 
 - Date of termination - If there is no date of termination, the last available FU date (including discharge) or the last SAE date (occurrence date), whichever occurs later. - If there is no follow-up and no adverse events : date of surgery or date of randomization, whichever occurs later.
Last study date	
Study Termination, Serious Adverse Event (SAE):
 
 1. For dead subjects: date of death 2. For alive subjects: 
 - Date of termination - If there is no date of termination, the last available FU date (including discharge) or the last SAE date (occurrence date), whichever occurs later. 
If there is no follow-up and no adverse events : date of surgery or date of randomization, whichever occurs later.

Study length (days)	
Study termination, Subject Information:
 
Last study date – Enroll Date+1

Extent of exposure (days)	
Last exposure date-surgery date+1

Late patients	
Subjects with more than 30 FU days of exposure

Patient-years	
Cumulative Study length (days)/365.25

Derived variable	Derivation algorithm
Early patient-years	Cumulative Study length (days) up to 30 days/365.25
Late patient-years	Cumulative Study length (days) from 31st day/365.25. Subjects with less than 31 FU days do not contribute to the late patient-years

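### Subjects lost to follow-up are censored at the discontinuation date rather than at last known MACCE status, which slightly favours non-inferiority in the supportive mITT Kaplan-Meier test

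*Protocol*

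**What the plan says.** - **When a subject discontinues.** CIP 8.5.5 lists among the reasons for ending participation: "The subject is deemed lost to follow up".
- **When a subject counts as lost.** CIP 18.1 (current text): "A subject will be considered lost to follow-up when all efforts to obtain information are unsuccessful". The minimum effort is three phone contacts and one certified letter.
- **Where the date is recorded.** CIP 18.1 says that for these subjects "a trial termination form will be filled out in order to document the date and reason for discontinuation".
- **Censoring rule.** SAP 5.2, time-to-event variables: "Subjects who have discontinued without an event will be censored at the date of discontinuation".
- **Derived dates.** For living subjects, Last study date in SAP Table 8 (section 18.12) is the termination date. The fallback is: "If there is no date of termination, the last available FU date (including discharge) or the last SAE date (occurrence date), whichever occurs later". Last exposure date follows the same order for living subjects who have not been explanted. Study length and patient-years are built on Last study date, and extent of exposure on Last exposure date.
- **Where the rule is used.** In SAP 10.4, "the one-year freedom from MACCE will be evaluated using the Kaplan-Meier estimates", with Greenwood standard errors and success if the statistic exceeds 1.96. The populations are stated: "This sensitivity analysis of non-inferiority will be assessed both in PP and mITT populations". SAP 11 (time to first MACCE, Cox model) and SAP 13.1.2 (time to onset of events, linearized late rates) also use censored follow-up or patient-years.
- **Visits.** The follow-up visit before one year falls between days 30 and 90. The one-year visit is at day 365 ± 30, so its window runs from day 335 to day 395 (CIP 8.7.1, SAP 5.4 and 9).

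**The concern.** Censoring is meant to remove a subject from the risk set when information stops. Here the subject leaves when the site gives up looking. For someone last seen at the 1-3 month visit, the absence may come to light only when the one-year visit is missed, and that visit is not overdue until day 395. A termination date entered then lies beyond day 365. The subject has by that point been carried as at risk and event-free for 275 to 335 days (365 − 90 and 365 − 30) during which MACCE status was not observed.

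The lost subjects belong to mITT, where the Kaplan-Meier test is meant to show that the result is robust to protocol deviations. Counting them as one-year successes raises estimated freedom from MACCE. The arm with more loss benefits more, and the trial is open-label. If more Perceval subjects are lost, the error favours non-inferiority.

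**Working it through.** **1. Does any text move the date back?** SAP 5.2 uses the discontinuation date. CIP 8.5.5 makes being deemed lost the discontinuation event, and CIP 18.1 allows that status only after the search has failed. Table 8 treats the termination date and the last follow-up date as different things and takes the former first. SAP 5.2 does not cite Table 8, but both point to the same date. No section sets censoring at last known MACCE status.

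**2. The plan's own figures.** These were checked by exact enumeration at the maximum N: 1234 × 0.9 / 2 ≈ 555 per-protocol subjects per arm, Normal(1.99, 3²) prior on the log-odds, threshold 0.9775, no interim looks.

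| True rates (control, Perceval) | Plan | Recomputed |
|---|---|---|
| 0.91, 0.91 | 0.805 | 0.817 |
| 0.88, 0.88 | 0.704 | 0.714 |
| 0.91, 0.86 | 0.023 | 0.0235 |
| 0.88, 0.83 | 0.025 | 0.0233 |

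The stated operating characteristics reproduce closely. They concern the primary analysis, which does not use this censoring rule.

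**3. Inputs for the effect.** From the documents: 91% freedom from MACCE, so 9% events; margin 0.05; 10% total attrition from enrolment to per-protocol. Assumed: the share lost between the 1-3 month and one-year visits, half of MACCE after day 90 (9% × 0.5 = 4.5%), lost subjects at average risk, and about 600 mITT subjects per arm.

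**4. Bias in one arm** = share lost × late MACCE risk.
- 3% lost: 0.03 × 0.045 = 0.00135, or 0.14 points
- 2%, 5% and 10% lost: 0.09, 0.23 and 0.45 points
- With 30% to 70% of events before last contact, the ranges are 0.05-0.13, 0.14-0.31 and 0.27-0.63 points

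Censoring at last contact brings each of these to zero.

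**5. Unequal loss: 4% Perceval, 1% control.**
- Shift in the difference: (0.04 − 0.01) × 0.045 = 0.00135, or 0.14 points, under 3% of the 5-point margin
- SE at 0.91 v 0.86: √(0.91 × 0.09/600 + 0.86 × 0.14/600) = 0.0184
- Rejection at the margin: Φ(−1.96 + 0.00135/0.0184) = Φ(−1.887) = 0.030, against 0.025

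This applies 4.5% late risk to both arms. At the margin Perceval has 14% MACCE, so 7% late on the same assumption. The shift is then 0.04 × 0.07 − 0.01 × 0.045 = 0.00235, and rejection is Φ(−1.96 + 0.128) = 0.033. The order of magnitude is unchanged.

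**6. Stress cases.** The Kaplan-Meier/Greenwood test was simulated at the margin with 617 per arm, 8000 trials and non-informative loss, with last contact at day 60.

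| Lost, control / Perceval | Rejects, termination date | Rejects, last contact |
|---|---|---|
| 0% / 0% | 0.029 | 0.029 |
| 5% / 5% | 0.032 | 0.027 |
| 10% / 10% | 0.036 | 0.025 |
| 2% / 8% | 0.046 | 0.026 |
| 0% / 10% | 0.057 | 0.029 |

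Monte Carlo error is about √(0.03 × 0.97/8000) = 0.002. The bottom three rows are extreme: they put up to the whole 10% attrition allowance of an arm into loss to follow-up, although that allowance also covers failed implants and other discontinuations.

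**The case against.** **The date is inferred.** CIP 18.1 does not say which date a site enters for a lost subject. It could be last contact, the last failed attempt or the day the form is completed. CRF instructions are given separately (CIP 8.7.1) and are not in the documents. If they require last contact, the problem disappears. This stands, and is why the conclusion is conditional. The written text still points to the later date.

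**The main analyses are protected.** A reader might infer that the primary conclusion is biased. The documents do not support that. The primary analysis is a binomial model without censoring, in a population defined by attendance to one year (CIP 10.4.4, SAP 6.5). The first sensitivity analysis in SAP 10.4 repeats it on mITT and imputes missing outcomes, conditional on the last intermediate time point known to be MACCE-free (SAP 15). Kaplan-Meier is therefore one of two non-inferiority checks on mITT.

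**Higher risk in lost subjects.** It is tempting to assume three times the risk. With 4% v 1% lost, the shift becomes 0.03 × 0.135 = 0.00405 and rejection Φ(−1.96 + 0.22) = 0.041. Most of that is informative loss, which last-contact censoring does not remove. After the change a shift of 0.00405 − 0.00135 = 0.0027 remains, and rejection is about 0.035. The 0.041 is not the cost of the censoring date.

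**Withdrawals.** A subject who withdraws is normally in contact at that moment, so the withdrawal date may be a date of known status. The argument is confined to loss to follow-up.

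**Conclusion.** The censoring rule is wrong as written for subjects lost to follow-up: the date it uses falls after MACCE status was last known, unless CRF instructions say otherwise. A subject last seen by day 90 can be counted as event-free at day 365. The error reaches the supportive mITT Kaplan-Meier test, the time-to-event curves, the Cox model and the patient-year denominators, and stops there.

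Its size is small under modest loss: about 0.14 points on one-year MACCE at 3% lost, and about 3.0% rejection instead of 2.5% at 4% v 1% lost. It becomes material only if loss is heavy or clearly unequal between arms. The share lost, the timing of last contact, the share of late events and average risk in lost subjects are all assumptions. The documents give only 10% total attrition. The point merits correction because it works against the purpose of a robustness check and is cheap to remove, not because it threatens the primary result.

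**What to change.** - **SAP 5.2:** for subjects terminated as lost to follow-up, censor at the last documented contact at which MACCE status was known (visit, phone call, physician report or SAE follow-up).
- **SAP Table 8:** derive Last study date and Last exposure date the same way for these subjects, so that patient-years agree with the curves.
- **Termination form (CIP 18.1):** record that date next to the administrative termination date.
- **Withdrawals:** keep the withdrawal date when MACCE status was documented at that contact.

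The cost is SAP wording, one derivation and one form field. Table 8 already uses visit and SAE dates as its fallback. Follow-up time becomes slightly shorter. Bias from higher risk among lost subjects would remain.

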1 LIST OF ABBREVIATIONS

ADE	Adverse Device Event
AE	Adverse Event
AI	Aortic Insufficiency
AS	Aortic Stenosis
AVR	Aortic Valve Replacement
CABG	Coronary Artery Bypass Graft
CCT	Cross Clamp Time
CCU	Cardiac Care Unit
CEC	Clinical Event Committee
CFR	Code of Federal Rules
CKMB	Creatine Kinase - MB
CPB	Cardio Pulmonary Bypass
CRF	Case Report Form
CT-Scan	Computerized Tomography Scan
DSMB	Data Safety Monitoring Board
DVI	Doppler Velocity Index
EC	Ethics Committee
ECG	Electrocardiogram
eCRF	electronic Case Report Form
EDC	Electronic Data Capture
EOA	Effective Orifice Area
EROA	Effective Regurgitant Orifice Area
FDA	Food and Drug Administration
GCP	Good Clinical Practices
IABP	Intra Aortic Balloon Pump
ICH	International Conference on Harmonization
ICU	Intensive Care Unit
IFU	Instructions For Use
IRB	Institutional Review Board
ISU	Independent Statistical Unit
ITT	Intention To Treat
LDH	Lactate DeHydrogenase
LVEF	Left Ventricle Ejection Fraction
LVOT	Left Ventricle Outflow Tract
MACCE	Major Cerebral And Cardiovascular Event
MAE	Major Adverse Event
MDR	Medical Device Reporting
MICS	Minimal Invasive Cardiac Surgery
MPG	Mean Pressure Gradient
mRS	modified Rankin Scale
NIHSS	NIH Stroke Scale/Score
NSTEMI	Non St-Elevation Myocardial Infarction
NYHA	New York Heart Association
OR	Operating Room
PP	Per Protocol
PPG	Peak Pressure Gradient
PPM	Patient Prosthesis Mismatch
PVL	Para Valvular Leak
QOL	Quality Of life Questionnaire
RBC	Red Blood Cell
SADE	Serious Adverse Device Effect
SAE	Serious Adverse Event
SC	Steering Committee
STEMI	ST-Elevation Myocardial Infarction
STS	Society of Thoracic Surgeons
SVD	Structural Valve Deterioration
TAVI	Transcatheter Aortic Valve Implantation
TEE	Trans Esophageal Echocardiogram
TTE	Trans Thoracic Echocardiogram
UADE	Unanticipated Adverse Device Effect
USADE	Unanticipated Serious Adverse Device Effect
VARC	Valve Academic Research Consortium
WBC	White Blood Cell

2 STUDY EXTENDED SYNOPSIS

Clinical Investigation Plan date	27 February 2018
Revision number	3.0
Title of trial	Perceval Sutureless Implant Vs Standard Aortic Valve Replacement (PERSIST-AVR) A Controlled Randomized Trial in the surgical treatment of Aortic Valve disease
Principal investigators	[name]., [name]., Ph.D.
Trial duration	Inclusion phase: from approximately 24 months to 30 months (2.5 years) according to sample size selection. Follow up phase: 5 years. Total duration time: from 7 to 7.5 years, depending on inclusion phase.
Planned trial period	The trial is expected to start in Q4-2015, once the relevant (inter)-national regulations/guidelines are fulfilled, including signed research agreements between the sites and Sponsor. The trial shall be completed after the 5-year follow-up of the last subject enrolled.
Number of trial centers planned	Approximately 60 sites worldwide
Study type	Non-inferiority post-market study
Trial design	Prospective, randomized (1:1), stratified, non blinded, multi-center, international
Primary objective:	The primary objective of this trial is to test the safety and efficacy of Perceval valve versus standard sutured stented bioprosthetic aortic valves among the intended trial population.
Secondary objectives:	To compare all relevant device and subject demographics, procedural and hospital discharge, short and long-term data, as described in the secondary endpoints section

Primary endpoint
	
The primary endpoint is freedom from MACCE (composite endpoint of all cause death, myocardial infarction, stroke, and valve re-intervention) at one year based on CEC adjudication


Secondary endpoints
	
 1. Surgical time 
 a. Cross clamp time during index procedure b. Cardiopulmonary bypass time during index procedure 2. Normalized Consumption Index and reduced Normalized Consumption Index, including resource consumption items such as (but not limited to): 
 a. Operative room time, b. Duration of ICU/CCU and total hospital stay c. Incidence of specific serious adverse events as defined in Appendix 3 d. Blood transfusion(s) 3. Quality of life questionnaire 
 b. At 1 month and 1 year post surgery 4. Intraprocedural and periprocedural serious adverse events regardless of relationship with the device within 72 hours 5. All valve and procedure relevant serious adverse as specified in VARC-2 guidelines [1] 
 a. Early safety at 30 days b. Clinical efficacy after 30 days c. Time related valve safety: SVD, endocarditis, thrombosis, thromboembolic events (excluding stroke), and bleeding annually up to 5 years 6. Serious device related adverse events up to 5 years 7. Freedom from MACCE at 2, 3, 4 and 5 years of follow up 8. Pacemaker implantation and cause up to 1 year 9. Valve hemodynamics (PPM, PPG, MPG; DVI, EOA, LVOT, AI, PVL,EROA) assessed by site-reported echocardiographic parameters preoperatively, at discharge, between 1-3 month, 1 year, 3 year and 5 year. 10. Valve hemodynamics (PPM, PPG, MPG; DVI, EOA, LVOT, AI, PVL,EROA) in a reduced cohort of patients assessed by core lab echocardiographic parameters preoperatively, at discharge, between 1-3 month, 1 year, 3 year and 5 year.

Trial population
	
All subjects with severe symptomatic aortic stenosis or steno-insufficiency who are candidates for surgical replacement of their native aortic valve according to established guidelines [2, 3] in current medical practice and as specified in the Perceval valve IFU.

Trial population criteria
	
Inclusion criteria
 
 1. The subject has an indication for treatment by valve replacement with a bioprosthesis according to the IFU, through either full sternotomy or mini-sternotomy.

	
 2. The subject has aortic valve disease that can be treated with a commercially available Perceval valve size, based on preoperative CT-scan. 3. The subject has: 
 a) critical aortic valve area defined as an initial aortic valve area of $\leq 1.0 \text{ cm}^2$ or aortic valve area index $< 0.6 \text{ cm}^2/\text{m}^2$ 
AND
 
 b) Mean gradient $> 40\text{mmHg}$ or $V_{\text{max}} > 4\text{m/sec}$ by resting echocardiogram or simultaneous pressure recordings at cardiac catheterization [or with dobutamine stress, if subject has a left ventricular ejection fraction (LVEF) $< 55\%$] or velocity ratio < 0.25; 4. The subject is symptomatic due to aortic stenosis with functional class of NYHA II or higher. 5. The subject has signed the informed consent. 6. The subject is of legal minimum age. 7. The subject will be available for postoperative follow-up beyond one year. 
Exclusion criteria
 
 1. The subject has a contraindication for treatment by the Perceval valve or by a bioprosthetic aortic valve as stated in the IFU. 2. The subject has aneurysmal dilation or dissection of the ascending aortic wall. 3. The subject is scheduled for concomitant procedures other than CABG, myectomy with or without aortic annulus enlargement. 4. The subject has congenital bicuspid (i.e. Sievers type 0) or unicuspid aortic valve. 5. Anatomical structures not suitable for Perceval valve such as: aortic root enlargement, where the ratio between the diameter of the sino-tubular junction and the annulus diameter is > 1.3. 6. The subject has a prosthetic heart valve in any position, including mitral valve repair. 7. The subject had a stroke or myocardial infarction (STEMI and NSTEMI) within 30 days prior to the planned valve implant surgery. 8. The subject has active endocarditis, myocarditis, or sepsis. 9. The subject is in cardiogenic shock manifested by low cardiac output and needing hemodynamic support. 10. The subject is allergic to nickel alloys. 11. The subject is already included in another clinical trial that could confound the results of this clinical investigation.
Number of subjects to be enrolled	A maximum of 1234 patients are planned to be enrolled, but accrual may stop earlier at approximately 900 or 1050 subjects.
Investigational device	Perceval sutureless aortic heart valve
Assessment schedule	
 • Subject inclusion (subject demography, surgery, hospital discharge)

	
 • 1-3 month post implant • 1 year post implant • Yearly up to 5 years

Statistical considerations
	
The study includes an adaptive approach for the determination of the study sample size.
 
Primary analysis
 
The primary study objective will be investigated by the primary analysis comparing the primary endpoint between the two randomized groups on PP population defined as all subjects without major protocol deviations and attending the scheduled follow-up visits up to 1 year at minimum.
 
A one-sided non-inferiority test will compare the two arms on the proportion of subjects that are event-free at one year.
 
The null hypothesis is that the 1-year freedom from MACCE in the Perceval arm is inferior to the 1-year freedom from MACCE in the Control arm:
 
 - $H_0: MACCE_{CONTROL} - MACCE_{PERCEVAL} \geq 0.05$ - $H_1: MACCE_{CONTROL} - MACCE_{PERCEVAL} < 0.05$ 
where $MACCE_j$ is the one-year event-free rate for arm j.
 
The primary analysis will use the Bayesian posterior probability that the difference (CONTROL – PERCEVAL valve) in 1 year MACCE event-free rates is lower than 0.05:
 $Pr(MACCE_{CONTROL} - MACCE_{PERCEVAL} < 0.05 Data)$ 
The null hypothesis will be rejected, and non-inferiority concluded, if the Bayesian posterior probability exceeds 0.9775 at the final analysis. This threshold was selected to control the Type I error rate at 2.5% (one-sided).
 
Non-inferiority will be assessed in the Per Protocol population as primary analysis. Sensitivity analyses on the primary endpoints will be performed using different assumptions and populations.
 
Interim Analysis and sample size determination
 
Total sample size for this trial will be adaptively determined through interim analyses to be performed when 900 and 1050 subjects will be enrolled. Accrual may stop earlier if there is at least 99.6% and 99.3% posterior probability of non-inferiority at the first and second interim analysis, respectively. The interim analysis will be conducted by an external Independent Statistical Unit (ISU) not involved in the study

	
conduct who will communicate to the Sponsor the decision on the continuation of enrollment.
 
Assuming a 91% event-free rate in both arms (based on blinded data review) this trial has 80.5% probability of success with a mean sample size of approximately 1129.
 
As the interim analysis objective simply focuses on patient recruitment, it will have no impact on subsequent study milestones. Therefore primary analysis will be performed at 12 months after last patient implanted and subject follow up will continue up to 5 years.
 
Other statistical analysis
 
Each component of the MACCE composite endpoint will be analyzed as proportion of subjects event-free at one year (95% C.I.) as well as using time-to-event methods. For Cox regression models, the stratification factors (country and surgical approach) and pre-operative variables (including demographic, medical history, and concomitant procedures) will be taken into account. All data collected up to cutoff date (eg. 12 months after last patient implanted) will be used for the time-to-event analysis.
 
Surgical times and Normalized Consumption Index endpoints will be analyzed in a superiority context. A one-sided superiority test will be conducted comparing the treatment and control group at discharge using appropriate regression models to account for stratification factors.
 
Number of serious adverse events and number of patients with at least one event will be presented in each group broken down by AE type. Number of events, as well as number and percentage of patients will be tabulated by timing (before / on or after intervention according to VARC-2 definitions).

--	--

